#### 10.1.1 Screening Period

The Screening Period is up to 4 weeks and includes a Screening phase and a Run-in phase.

### 10.1.1.1 Screening Phase

The Screening Phase will be up to 2 weeks in duration and includes Visit 1 (Week -4) only. The Screening Phase must be long enough to collect the data to establish whether the patient satisfies the inclusion/exclusion criteria.

Patients will undergo Screening assessments at Visit 1 (Week -4) following signing of the ICF. Patients who meet the inclusion criteria as noted in [Section 7.1](#) and meet no exclusion criteria as noted in [Section 7.2](#) will be randomized at Visit 3 (Day 1).

The IRT will be contacted at Visit 1 for notification of Screening Visit and to obtain the patient number.

In cases where original screen failure was due to reasons expected to change at rescreening and based upon the Investigator's clinical judgment, the patient can be rescreened once prior to entering the Run-in Phase of this study. In these cases, a patient will need to sign a new ICF, be registered as a rescreened in IRT, and assigned a new patient number in IRT (first Screening Visit is to be registered as screen failure in IRT), and complete Screening Visit procedures and assessments again.

#### 10.1.1.1.1 Screening Visit, Visit 1 (Week -4)

The following procedures/assessments will be performed at Visit 1 (Week -4):

- Obtain informed consent:
  - The patient will receive verbal information concerning the aims and methods of the study, its constraints and risks, and the study duration. Written information will be provided to the patient. Written informed consent must be signed by the patient and Investigator prior to any investigations.
  - 
- IRT notification (allocation of ID, registration of Screening).
- Assessment of inclusion/exclusion criteria.
- Collection of demographic data (age, gender, race, and ethnic origin).
- Assessment of the patient's medical and surgical history, including history, treatment and complications (eye, kidney, history of smoking/tobacco use, history of alcohol, and history of amputation events, etc) of T2D.
- Concomitant medication and medication history, including any prior medications for T2D.
- Measurement of BW and height.
- Complete physical examination including vital signs (SBP and DBP, HR, temperature, and respiratory rate) (see [Appendix C](#) for details).
- The following laboratory testing (by the central laboratory):
  - Serum 25-hydroxyvitamin D.

- HbA1c.
- Serum FSH and estradiol (for documentation of menopausal status).
- Clinical chemistry (including amylase, lipase) and hematology.
- AEs/SAEs/AESI/EOSI and hypoglycemia (if any) are reported.
- Urinalysis (dipstick and microscopy).
- Patients will be instructed to return to the site in the fasting state for Visit 3 (Week 0).

#### **10.1.1.2 Run-in Phase**

The Run-in Phase is 2 weeks in duration and includes Visit 2 (Week -2). As an exception, if justified according to the Investigator's assessment, the Run-in period can be extended up to a maximum of 14 additional days to complete all the eligibility assessments prior to the randomization.

##### **10.1.1.2.1 Run-in Visit, Visit 2 (Week -2)**

The following procedures/assessments will be performed at Visit 2 (Week -2):

- Exclusion criteria are to be reviewed.
- Changes in concomitant medication are reviewed.
- Measurement of BW.
- Abbreviated physical examination.
  - The abbreviated physical examination should focus on cardiac and respiratory systems, (as well as any areas important for assessment of AEs, if necessary), and vital signs (SBP and DBP, and HR) (see [Appendix C](#) for details).
  - Diet and exercise instruction will be provided.
- Blood glucose meter is dispensed and instructions/training are provided.
- Patient diary is dispensed and instructions/training are provided.
- Instruction on glucose testing, basic genito-urinary (GU) hygiene and hydration, and recognizing DKA symptoms (see [Appendix B](#)) is provided.
- The IRT is notified for registration of Run-in Visit and allocation of single-blind Run-in kit.
- Run-in kit/placebo is dispensed.
- 12-lead ECG is conducted.
- AEs/SAEs/AESI/EOSI and hypoglycemia (if any) are reported.
- Patients are instructed to return to the site in the fasting state with used, partially used, or not used single-blind Run-in kit for Visit 3 (Randomization).

- Patients will be referred to DXA scan facility to perform DXA scan prior to Visit 3 (Randomization).
- Patients are provided with a urine container and instructed on how to collect 24-hour urine at home to be brought to the site at Visit 3 (Randomization).

### **10.1.2 Randomized Double-blind Core Treatment Period (Day 1 to Week 26)**

Upon successful completion of the Run-in Phase, patients will be randomly allocated to either sotagliflozin 400 mg, sotagliflozin 200 mg, or sotagliflozin-matching placebo for the entire duration of the 104 weeks of Double-blind treatment. The first 26 weeks after the randomization correspond to the Core Treatment Period. All randomized patients will be followed at regular on-site visits for the duration of the treatment period.

In addition to routine laboratory testing, the following will be performed at specified time points: [REDACTED]; collection of home 24-hour urine for assessment of albumin, creatinine, calcium (adjusted for creatinine), phosphorus (adjusted for serum phosphorus and creatinine), magnesium (adjusted for serum magnesium and urinary creatinine).

In the event of abnormal urinalysis findings suspicious of UTI, urine culture should be performed. Positive urine culture determination will be based upon the criteria of the reporting laboratory. Additionally, urine culture should be performed if at any point the Investigator suspects the presence of a UTI.

#### **10.1.2.1 Randomization (Baseline Day 1/Visit 3/Week 0)**

The following procedures will be performed at this visit:

- Exclusion criteria are to be reviewed, including review of DXA results for eligibility, and assessment of compliance with single-blind IMP treatment during Run-in Phase.
- Concomitant medications are reviewed.
- Measurement of BW.
- Abbreviated physical examination and vital signs (see [Appendix C](#)).
- IRT to be notified and randomization to occur.
- AEs/SAEs/AESI/EOSI and hypoglycemia (if any) are reported.
- Diet and exercise instruction.
- Patient diary collected and reviewed and a new one is dispensed. Instructions/training are provided as needed.
- Instructions on glucose testing, basic GU hygiene, hydration, and DKA symptoms are provided.
- SMBG records will be reviewed.

- The following laboratory testing (by the central laboratory):
  - FPG.
  - HbA1c.
  - Clinical chemistry (including amylase, lipase) and fasting lipids.
  - Hematology.
  - Serum estradiol (only for women).
  - Bone turnover markers.
  - Markers of calcium metabolism.
  - Urinalysis (dipstick and microscopy).
  - Albumin, creatinine, calcium, phosphorus, and magnesium concentration in 24-hour urine.
- Collection of samples for additional laboratory testing:
  - [REDACTED]
- IRT will be notified IMP for resupply.
- Double-blind IMP is dispensed.
- Patients are instructed to return to the site in the fasting state for their next visit.
- For accountability and compliance purposes, patients are instructed to return to the site at the next visit bringing their used, partially used, or not used medication kit(s).

#### **10.1.2.2 On-site visits from Visit 4 to Visit 7 (Week 3 to Week 18)**

The following procedures will be performed at study visits from Week 3 to Week 18:

- Concomitant medications will be assessed.
- Measurement of BW.
- Abbreviated physical examination and vital signs (see [Appendix C](#)).
- IMP accountability and compliance with double-blind IMP treatment.
- IRT will be notified for IMP resupply.
- AEs/SAEs/AESI/EOSI and hypoglycemia (if any) occurring since the previous visit will be reported.
- Patient diary will be collected and reviewed and a new one will be dispensed. Instructions/training will be provided as needed.
- SMBG records will be reviewed.
- Patients will be evaluated for glycemic rescue.

- Instructions on glucose testing, basic GU hygiene, hydration, and recognizing DKA symptoms will be provided (see [Appendix B](#)).
- Central laboratory testing:
  - FPG: Visit 4 (Week 3), Visit 5 (Week 6), and Visit 6 (Week 12).
  - HbA1c: Visit 6 (Week 12) only.
  - Clinical chemistry: Visit 4 (Week 3), Visit 5 (Week 6), and Visit 6 (Week 12).
  - Hematology: Visit 6 (Week 12) only.
  - Urinalysis (dipstick and microscopy): Visit 6 (Week 12) only.
  - [REDACTED]
- IMP is dispensed.
- Patients are instructed to return to the site in the fasting state for the next visit, except for Visit 7 (Week 18) when fasting is not required.
- For accountability and compliance purposes, patients are instructed to return to the site at the next visit bringing their used, partially used, or not used medication kit(s).
- At Visit 7 (Week 18) patients will be referred to DXA scan facility to perform DXA scan within 2 weeks prior to Visit 8 (Week 26).
- At Visit 7 (Week 18) patients will be provided with a urine container and instructed on how to collect 24-hour urine at home to be brought to the site at the next visit.

#### **10.1.2.3 On-site Visit 8 (Week 26) - End of Randomized Double-blind Core Treatment Period**

The following procedures will be performed at this visit:

- Concomitant medications will be reviewed.
- Measurement of BW.
- Complete physical examination and vital signs (see [Appendix C](#)).
- IMP accountability and compliance with double-blind IMP treatment.
- IRT will be notified for IMP resupply.
- AEs/SAEs/AESI/EOSI and hypoglycemia (if any) occurring since the previous visit will be reported.
- Diet and exercise instruction will be provided.
- Patient diary will be collected and reviewed and a new one will be dispensed. Instructions/training will be provided as needed.
- SMBG records will be reviewed.
- Patients will be evaluated for glycemic rescue.

- Instructions on glucose testing, basic GU hygiene, hydration, and recognizing DKA symptoms will be provided (see [Appendix B](#)).
- 12-lead ECG.
- Central laboratory testing:
  - FPG.
  - HbA1c.
  - Clinical chemistry.
  - Hematology.
  - Fasting lipids.
  - Serum estradiol (only for women).
  - Bone turnover markers.
  - Markers of calcium metabolism.
  - Urinalysis (dipstick and microscopy).
  - Albumin, creatinine, calcium, phosphorus, and magnesium concentration in 24-hour urine.
- 
- Double-blind IMP is dispensed.
- Confirm with the central review facility that the DXA procedures for Visit 8 (Week 26) were performed successfully. In case the DXA scan needs to be repeated, or has not been done yet, instruct the patients to perform the DXA scan within the next 7 days.
- For accountability and compliance purposes, patients are instructed to return to the site at the next visit bringing their used, partially used, or not used medication kit(s).

### **10.1.3 Double-blind, Randomized Extension Period (Week 27 to Week 104)**

#### **10.1.3.1 On-site visits from Visit 9 to Visit 12 (Week 27 to Week 86)**

The following procedures will be performed at each Visit, except as specified:

- Concomitant medications will be assessed.
- Measurement of BW.
- Measurement of height only at Visit 10 (Week 52).
- Abbreviated physical examination and vital signs (see [Appendix C](#)).
- IMP accountability and compliance with double-blind IMP treatment.
- IRT will be notified for IMP resupply.

- AEs/SAEs/AESI/EOSI and hypoglycemia (if any) occurring since the previous visit will be reported.
- Diet and exercise instruction will be provided, except at Visit 9 (Week 39).
- Patient diary will be collected and reviewed and a new one will be dispensed. Instructions/training will be provided as needed.
- SMBG records will be reviewed.
- Patients will be evaluated for glycemc rescue.
- Instructions on glucose testing, basic GU hygiene, hydration, and recognizing DKA symptoms will be provided.
- Central laboratory testing:
  - FPG: Visit 10 (Week 52) and Visit 12 (Week 86).
  - HbA1c: Visit 10 (Week 52) and Visit 12 (Week 86).
  - Clinical chemistry, including amylase and lipase: Visit 10 (Week 52) and Visit 12 (Week 86).
  - Hematology: Visit 10 (Week 52) and Visit 12 (Week 86).
  - Serum estradiol (only for women): Visit 10 (Week 52).
  - Bone turnover markers: Visit 10 (Week 52).
  - Markers of calcium metabolism: Visit 10 (Week 52).
  - Urinalysis (dipstick and microscopy): Visit 10 (Week 52) and Visit 12 (Week 86).
  - Albumin, creatinine, calcium, phosphorus, and magnesium concentration in 24-hour urine will be done at Visit 10 (Week 52).
- Double-blind IMP is dispensed.
- At Visit 10 (Week 52) confirm with the central review facility that the DXA procedures for Visit 8 were performed successfully. In case the DXA scan needs to be repeated, or has not been done yet, instruct the patients to perform the DXA scan within the next 7 days.
- Patients are instructed to return to the site in the fasting state for the next visit, except for Visit 9 (Week 39) and Visit 11 (Week 68) when fasting is not required.
- For accountability and compliance purposes, patients are instructed to return to the site at the next visit bringing their used, partially used, or not used medication kit(s).
- At Visit 9 (Week 39) and at Visit 12 (Week 86), patients will be referred to DXA scan facility to perform DXA scan within 2 weeks prior to the next visit.
- At Visit 9 (Week 39) and at Visit 12 (Week 86) patients will be provided with a urine container and instructed on how to collect 24-hour urine at home to be brought to the site at the next visit.

### **10.1.3.2 On-site Visit 13 (Week 104) - End of treatment (EOT)**

The following procedures will be performed at this Visit:

- Concomitant medications will be reviewed.
- Measurement of BW and height.
- Complete physical examination will be done and vital signs (see [Appendix C](#)).
- IMP accountability and compliance with double-blind IMP treatment.
- IRT will be notified for end of treatment.
- AEs/SAEs/AESI/EOSI and hypoglycemia (if any) occurring since the previous visit will be reported.
- Patient diary will be collected and reviewed and a new one will be dispensed.
- SMBG records will be reviewed.
- 12-lead ECG.
- Central laboratory testing:
  - FPG.
  - HbA1c.
  - Clinical chemistry, including amylase, lipase, and fasting lipids.
  - Hematology.
  - Serum estradiol (only for women).
  - Bone turnover markers.
  - Markers of calcium metabolism.
  - Urinalysis (dipstick and microscopy).
  - Albumin, creatinine, calcium, phosphorus, and magnesium concentration in 24-hour urine.
- Confirm with the central review facility that the DXA procedures for Visit 13 (Week 104) were performed successfully. In case the DXA scan needs to be repeated, or has not been done yet, instruct the patients to perform the DXA scan within the next 7 days.
- Patients are instructed to return to the site in 2 weeks for the follow-up visit.
- Patients are instructed to return to the site in the fasting state for the next visit.

### **10.1.4 Post-treatment follow-up period**

The post-treatment Follow-up Period will include an on-site visit, 2 weeks  $\pm$  3 days after the last dose of IMP.

#### **10.1.4.1 Follow-up Visit (Week 106/Visit 14)**

The following procedures will be performed at this visit:

- Concomitant medications will be reviewed.
- Measurement of BW.
- Abbreviated physical examination including vital signs (see [Appendix C](#)).
- IRT to be notified of End of Study.
- AEs/SAEs/AESI/EOSI and hypoglycemia (if any) since the previous visit will be reported.
- Collect glucose meter.
- Patient diary is collected and reviewed.
- The patient is instructed to schedule future follow-up with their health care provider.
- SMBG records will be reviewed.
- Central laboratory testing.
  - Hematology.
  - Clinical chemistry (including amylase and lipase).

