### **6.2.2 Early termination**

If a patient discontinues treatment with the IMP at any time during the Randomized Double-blind Core Treatment Period or during the Randomized Double-blind Extension Treatment Period, the patient will have a Premature EOT visit, and a Follow-up Visit, 2 weeks after the last dose of IMP. In addition, every effort will be made to have the patients return to the site at the time corresponding to their scheduled visits, particularly the Week 26 Visit and Week 104 visit to perform the respective study assessments, emphasizing the measurement of HbA1c and BMD. If the patient does not agree to site visits, he or she will be contacted by respective sites by telephone to inquire about safety status.

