## 10 STUDY PROCEDURES

### 10.1 VISIT SCHEDULE

The visit schedule and procedures/assessments are listed in the Study Flow Chart ([Section 1.2](#)). The aim of this section is to provide details on how some of the procedures/assessments should be performed.

This is an out-patient study and consists of 14 on-site visits. Additional on-site visits or telephone contacts can be scheduled at any time during the study whenever considered necessary by the Investigator.

The patients need to arrive at the study site in a fasting state for Visit 1, Visit 3, Visit 4, Visit 5, Visit 6, Visit 8, Visit 10, Visit 12, Visit 13, and Visit 14 unless instructed otherwise by the investigator. Throughout the study, “fasting” is defined as at least 8 hours without food (no food or liquid intake, other than water). **Note:** If the patient is not fasting at the visits specified above, the blood sample will not be collected and a new appointment should be given to the patient for the following day if possible, with instruction to be fasted. Other procedures can be performed as scheduled. All laboratory assessments will occur prior to IMP and NIMP administration on the day of the visit.

The Run-in Visit (Visit 2) can be performed up to 2 weeks ( $\pm 3$ ) days after the Screening Visit and once the results of all Screening tests are available and the patient is confirmed to be eligible for participation in the study. The visit windows for the Double-blind Treatment Period visits will be as follows: Visit 3 through Visit 8 should occur at the schedule  $\pm 3$  days; Visit 9 through Visit 12 should occur at the schedule  $\pm 7$  days. Visit 13 should occur at the schedule  $\pm 3$  days and Follow-up Visit (Visit 14) should occur within 2 weeks after last dose of IMP  $\pm 3$  days.

If one visit date is changed, the next visit should occur according to the original schedule, ie, calculated from the date of Baseline visit (Visit 3, Week 0).

For a complete list of procedures scheduled for each study visit please refer to the Study Flow Chart ([Section 1.2](#)), which details the procedures to be performed.

All data obtained during the study visits are reviewed by the Investigator and Sub-investigators who are qualified in treatment of T2D and are trained on the study.

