#### **10.3.4 Handling of patients after permanent treatment discontinuation**

Every effort should be made to maintain patients in the study. Patients will be followed-up according to the study procedures specified in this protocol up to the scheduled date of study completion, or up to recovery or stabilization of any AE to be followed-up as specified in this protocol, whichever comes last.

If a patient decides to discontinue study treatment early, a Premature EOT Visit (see [Section 10.1.3.2](#)) should be scheduled prior to treatment discontinuation, if possible. If not possible, the Premature EOT Visit should be scheduled as soon as possible after the permanent treatment discontinuation and the patients will be assessed using the procedure normally planned for the last dosing day with the IMP. For patients that discontinue treatment but remain in the study, remaining study visits should occur as scheduled, as possible. The IRT should be notified of the EOT.

All cases of permanent treatment discontinuation must be recorded by the Investigator in the appropriate pages of the eCRF.

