2.4.4.1 Analysis of primary efficacy endpoint(s)

Primary analysis

The primary efficacy endpoint of change in HbA1c from Baseline to Week 26 will be analyzed by an Analysis of Covariance (ANCOVA) model using HbA1c values measured at Baseline and Week 26 (observed or imputed). The missing data at endpoint will be imputed by multiple imputation (MI) methods as detailed below. To be concise, the following texts related to imputation are generalized to accommodate primary as well as continuous secondary efficacy endpoints.

Missing endpoint data at Week 26 (or Week 12 for SBP) visit will be imputed using a model built separately in each treatment group and estimated from the patients in the same treatment group who prematurely discontinue the IMP before the Week 26 (or Week 12 for SBP) visit but have the measurement for the endpoint (ie, retrieved dropouts). The imputation model will include the randomization strata and the corresponding baseline value. In cases of non-convergence during the imputations, the offending stratum will be identified and then will be dropped from the model. Considering that the number of retrieved dropout patients in each treatment group is expected to be small, a simple imputation model based on regression will be used with baseline measurement included as the predictor. This will serve as the primary method of imputation for missing data should sampling criteria be satisfied (see below).

An alternative (back-up) imputation method will be used if the number of patients who prematurely discontinue the IMP before the Week 26 (or Week 12 for SBP) visit but have the measurement for the endpoint is < 5 in any treatment groups (ie, an insufficient number of retrieved dropouts to support the imputation method described above). This criterion will be assessed for each primary or continuous secondary efficacy endpoint.

In the back-up imputation method, missing post-Baseline endpoint values at Week 26 (or Week 12 for SBP) will be imputed by the washout Multiple Imputation (MI) method under the missing not at random (MNAR) framework.

Missing endpoint data at the Week 26 (or Week 12 for SBP) in all treatment groups (sotagliflozin 400 mg, sotagliflozin 200 mg and placebo) are imputed from a model estimated from patients in the placebo group who have the endpoint data available.

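### The only Follow-up Visit list registers End of Study two weeks after the last dose, with no exception for patients who stop drug early but are meant to stay to Week 104

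*Protocol*

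**What the plan says.** **Timing.** Protocol 6.1.4 gives the Follow-up Visit to all patients, after a scheduled or a premature end-of-treatment visit. For early stoppers, 6.2.2 says "the patient will have a Premature EOT visit, and a Follow-up Visit, 2 weeks after the last dose of IMP", and 10.3.3 repeats this. Section 10.1.4 opens with "The post-treatment Follow-up Period will include an on-site visit, 2 weeks" (±3 days, counted from the last dose). Section 10.1 ties the visit number itself to the last dose: "Follow-up Visit (Visit 14) should occur within 2 weeks after last dose of IMP".

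**Content.** Protocol 10.1.4.1 is the only list of procedures for this visit. Among its steps are "IRT to be notified of End of Study", "Collect glucose meter" and "The patient is instructed to schedule future follow-up with their health care provider". None is limited to completers.

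**Retention.** Protocol 10.3.4 says: "For patients that discontinue treatment but remain in the study, remaining study visits should occur as scheduled, as possible". Sections 6.2.2 and 10.3.3 single out the Week 26 and Week 104 visits, and 6.2.2 stresses HbA1c and BMD. Section 10.4.2 continues observation to the end of the study after early discontinuation. SAP 1.1 expects these patients to keep contributing assessments until the last planned visit. For the IRT, 10.3.4 asks only that the end of treatment be notified.

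**Glucose monitoring.** The flow chart (Protocol 1.2) has SMBG at every visit from Visit 3 to Visit 14. Protocol 8.2.2 and 9.2.1.8 rely on fasting SMBG up to Week 104.

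**The concern.** For a patient who stops IMP early and agrees to stay, the two sets of instructions pull apart. One tells the site to register End of Study and take back the meter about two weeks after the last dose. The other tells it to keep seeing the patient, and to keep reviewing SMBG, for up to two years.

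The SAP gives these patients a particular role. Its first-choice imputation for HbA1c, body weight, FPG and SBP (SAP 2.4.4.1) is estimated, within each arm, only from patients "who prematurely discontinue the IMP before the Week 26 (or Week 12 for SBP) visit but have the measurement for the endpoint". SAP 2.4.5.1 does the same for BMD at Weeks 26, 52 and 104. A patient closed out at the Follow-up Visit changes from a source of information for that model into a missing value to be imputed by it. If any arm has fewer than 5 such patients, the efficacy analysis moves to the washout method. If there are too few for BMD, the pattern-based method becomes primary.

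**Working it through.** No stated figure is in dispute, so the first part of the check sets the texts against each other.

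**1. Follow one patient through the text.** Take a patient whose last dose is at Week 10.
- The Premature EOT Visit uses the list in Protocol 10.1.3.2, because 10.3.4 refers there, although that list is headed Visit 13 (Week 104).
- That list tells the patient to return in 2 weeks for the follow-up visit.
- The Follow-up Visit therefore falls at about Week 10 + 2 = Week 12, and its only list is 10.1.4.1.
- Followed as written, End of Study is notified at Week 12, which is 26 − 12 = 14 weeks before the primary endpoint and 104 − 12 = 92 weeks before the last treatment-period visit.
- Sections 6.2.2, 10.3.3 and 10.3.4 still expect this patient at Week 26 and Week 104.

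**2. Compare step by step for an early stopper who remains in the study.**

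| Item | Follow-up list (10.1.4.1) | Rules for early stoppers |
|---|---|---|
| IRT | End of Study notified | Only end of treatment notified (10.3.4) |
| Glucose meter | Collected | SMBG at later visits (1.2), with thresholds to Week 104 (8.2.2, 9.2.1.8) |
| Later visits | Not mentioned | Continue as scheduled (10.3.4) |

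The first two rows conflict. The third is an omission.

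**3. How sensitive is the imputation rule to lost returns?** The SAP threshold is 5 retrieved dropouts in each of 3 arms. The documents give neither the number of early stoppers nor the share who return, so both are assumptions here. Let m be the early stoppers per arm and r the chance that each has a Week 26 value, independent and equal across arms:

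P(some arm below 5) = 1 − [P(X ≥ 5)]³, with X ~ Binomial(m, r).

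For m = 12 (10% of 120):
- r = 0.75: P(X ≥ 5) = 0.9972, giving 0.008, about 1%.
- r = 0.50: P(X ≥ 5) = 1 − (1 + 12 + 66 + 220 + 495)/4096 = 0.806, giving 1 − 0.806³ = 0.476, about 48%.
- r = 0.25: P(X ≥ 5) = 0.158, giving 0.996, or 99.6%.

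Varying m:

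| m per arm | r = 0.75 | r = 0.50 | r = 0.25 |
|---|---|---|---|
| 6 | 85% | 99.9% | >99.9% |
| 12 | 1% | 48% | 99.6% |
| 18 | <0.1% | 5% | 89% |

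The result depends heavily on both assumptions. With 6 stoppers per arm the threshold would probably be missed even with good return. With 12 or 18, return is what decides. The table shows how much retention matters to the SAP rule. It does not estimate what 10.1.4.1 would do to retention.

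**The case against.** The best defence is that the list was written for completers. Its heading reads Week 106/Visit 14, it follows the Week 104 visit, and early stoppers have their own section, 10.3. The intention to retain them is explicit and repeated (6.2.2, 10.3, 10.3.3, 10.3.4, 10.4.2, SAP 1.1), and 9.2.1.3 collects safety data to the scheduled study end. Protocol 6.1.4 describes the purpose of the Follow-up Visit as collecting safety information. A sensible site would probably read 10.1.4.1 in that light. This stands as evidence of intent and limits the weight of the point. It does not remove the conflict: 10.1 and 10.1.4 define the visit by last dose, 6.1.4 applies it to everyone, 10.3.4 already sends early stoppers to a list labelled Week 104, and there is no other Follow-up list.

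A reader might infer more than the text supports:
- **That an End-of-Study entry in the IRT prevents later visits or sampling.** No section says so. After randomization the visit lists use the IRT for resupply and for registering the end of treatment. The SAP (2.1.4) takes the end of study from the last scheduled visit or an e-CRF page, not from the IRT.
- **That the referral step ends trial attendance.** Telling a patient to arrange follow-up with a provider does not tell them to miss study visits.
- **That every endpoint is lost.** In the Week 10 example the Follow-up Visit records vital signs and body weight at about Day 84, inside the Week 12 analysis window (Days 63 to 104, SAP 2.5.4), so loss of SBP does not follow.
- **That fracture follow-up stops.** Telephone safety contact is foreseen for patients who decline site visits (6.2.2, 10.3.3).
- **That the primary analysis would be undermined.** The washout method is prespecified, and SAP 2.4.4.1 reports it as a sensitivity analysis when the retrieved-dropout method is primary.

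**Conclusion.** The conflict is real and lies in the wording: the one list that governs the Follow-up Visit contains two close-out steps, End-of-Study notification and meter collection, that do not fit patients who have stopped drug and remain in the study. It is an unreconciled procedure list and does not show that the retention plan was changed or that the design is at fault.

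The consequence is conditional. If sites apply the list literally, potential retrieved dropouts could be lost at Week 26, and for BMD also at Weeks 52 and 104. Under the assumption of 12 early stoppers per arm, the chance of missing the SAP threshold for HbA1c runs from about 1% (75% return) through 48% (50%) to 99.6% (25%). How many patients stop, how many return, and how sites and the IRT behave are not in the documents, so actual loss is unknown. A claim that the primary method will switch would go beyond them. The importance is minor to moderate.

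**What to change.** Reconcile Protocol 10.1.4.1 with 10.3.4:
- State that End-of-Study IRT notification and glucose-meter collection apply only at the patient's last study visit. For completers this is Visit 14. For patients who stopped IMP early it is the last scheduled visit attended, or withdrawal of consent for follow-up.
- State that for early stoppers who remain in the study, the 2-week Follow-up Visit collects safety data and only the end of treatment is registered in the IRT, as 10.3.4 already provides.

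The cost is a short wording change and a check that IRT visit status follows it. No visits or procedures are added. How glucose is monitored and when rescue applies are left as the Protocol has them.
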